Protocol study and Statistical analysis plan

Effect of Parenting Training on Quality of Life and Parenting in Parents Who Have Children with Intellectual Disabilities

20 December 2024

Design

This study used a quasi-experimental design, which was conducted based on a pretest-posttest control group.

Samples

One hundred and forty-one mothers with ID children attending special schools in East Java, Indonesia, were recruited and divided into intervention (N=71) and control group (N = 70) according to a special school using a convenience sampling method. We estimated that a minimum of 60 participants in each group would be required using the G.power 3.1.9.7 application, with an effect size of 0.335, and a power of the test $(1-\beta) = 80\%$. The inclusion criteria were

- having a child aged 7-18 years who has mild and moderate intellectual disabilities
- living in the same house as a child with intellectual disabilities,
- being able to communicate fluently

The exclusion criteria were

- having disabilities
- having a child with intellectual disabilities who has a chronic disease
- having a child with intellectual disabilities and other disabilities

Instrument

Parenting quality was evaluated using the Parenting Sense of Competence (PSOC) developed by Gibaud-Wallston and Wandersman, adapted from Johnston and Marsh (Cronbach Alpha=0.79) (Johnston & Mash, 1989). Quality of life was evaluated using the World Health Organization Quality of Life (WHOQOL-BREF) (Cronbach Alpha= 0.66-0.8) developed by the WHO (Group, 1994). The WHOQOL-BREF consists of four domains (physical health, psychological, social relationships, and environment) with 26 questions. The total score for each domain is transformed to a scale of 0-100 according to the scoring guidelines. The PSOC consists of the domains of satisfaction and self-efficacy with parenting, which are assessed with 16 questions, with a satisfaction score ranging from 9 to 54 and a self-efficacy score from 7 to 42.

Intervention

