The control and intervention groups were given a parenting guidebook for children with ID. The intervention group received approximately three hours of parenting training once a week for 5 weeks. The intervention group received parenting training focused on understanding children with ID in the first week, practical parenting skills in the second week, and how to provide emotional support and regulate parental emotions in the third week. Knowledge and skills were reinforced in the fourth and fifth weeks. The intervention group received training in small groups, each consisting of only 10 participants. The training involved experts in mental health counseling, pediatric nurses, special school teachers, and a motivator.

Data Collection

The PSOC and WHOQOL scores were measured by a researcher who was not blinded to the study from January to August 2025 at the school.

Data analysis:

SPSS version 23 was used to analyze the data. Categorical variables were reported as frequencies and percentages. Continuous variables were reported as median and standard deviation (SD). The Kolmogorov-Smirnov test was used to confirm normal distribution. The Wilcoxon and Mann-Whitney U tests were used for continuous variables with non-normal distributions, as well as the Chi-squared test for qualitative variables. The Wilcoxon and Mann-Whitney U tests were used for continuous variables with non-normal distributions. A p-value of less than 0.05 was considered statistically significant. The point-biserial correlation test was used to evaluate the effect size. SPSS version 23 was used to analyze the data. Categorical variables were reported as frequencies and percentages. Continuous variables were reported as median and standard deviation (SD). The Kolmogorov-Smirnov test was used to confirm normal distribution. The Wilcoxon and Mann-Whitney U tests were used for continuous variables with non-normal distributions, as well as the Chi-squared test for qualitative variables. The Wilcoxon and Mann-Whitney U tests were used for continuous variables with non-normal distributions. A p-value of less than 0.05 was considered statistically significant. The point-biserial correlation test was used to evaluate the effect size.

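### Continuous scores are summarised as median with SD, and the only between-group effect size is a unitless correlation with no confidence interval and no adjustment for the pretest

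*Combined protocol and SAP*

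**What the plan says.** All references are to the combined protocol and SAP.

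- **Summaries (Data analysis):** "Continuous variables were reported as median and standard deviation (SD"). No condition is attached.
- **Normality (Data analysis):** "The Kolmogorov-Smirnov test was used to confirm normal distribution". The result is not linked to the choice of summary or effect size.
- **Tests (Data analysis):** "The Wilcoxon and Mann-Whitney U tests were used for continuous variables with non-normal distributions".
- **Effect size (Data analysis):** "The point-biserial correlation test was used to evaluate the effect size". No other measure is named. The plan does not say whether it is computed on posttest or change scores.
- **Scales (Instrument):** for the WHOQOL-BREF, "The total score for each domain is transformed to a scale of 0-100 according to the scoring guidelines"; for the PSOC, "with a satisfaction score ranging from 9 to 54 and a self-efficacy score from 7 to 42".
- **Design and Samples:** "This study used a quasi-experimental design, which was conducted based on a pretest-posttest control group", with 71 and 70 mothers divided "according to a special school using a convenience sampling method".

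The analysis paragraph is printed twice in the same words, so neither copy corrects the other. Nowhere do the documents mention an interquartile range, a confidence interval, or a between-group difference in score points, adjusted or not.

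**The concern.** An SD measures spread around a mean. Beside a median it does not describe where the data lie, and the mismatch is greatest for skewed scores, the case in which the plan turns to rank tests. If 'median' was meant to be 'mean', the sentence still mislabels the number that readers will see.

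The larger matter is the between-group estimate. The point-biserial correlation is a rescaled mean difference: unitless, unadjusted and, as planned, without a measure of precision. The groups were not randomised. They were formed by school, so they may differ before training starts. The design collects a pretest that could correct for this, yet no stated between-group estimate uses it. At stake is whether readers can see how far training moved each score, net of where the groups began, and how uncertain that figure is.

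**Working it through.** The plan gives no figure for this point; its one calculated figure, 60 per group, plays no part. From Samples: n1 = 71, n2 = 70, N = 141. SDs, skewness and the pre-post correlation (rho) are not given, so all values for them below are assumptions. The intervals treat mothers as independent.

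**1. Median with SD on a 0-100 scale.** For normal scores, 16% lie beyond one SD on each side. Two skewed shapes for comparison:

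| Assumed shape | Mean | Median | SD | Below median - SD | Above median + SD | Quartiles |
|---|---|---|---|---|---|---|
| Beta(5, 2), skew -0.60 | 71.4 | 73.6 | 16.0 | 19.8% | 12.4% | 61.1, 83.9 |
| Beta(8, 1.2), skew -1.25 | 87.0 | 89.6 | 10.5 | 20.0% | 0% | 81.5, 95.1 |

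In the second row median + SD is 100.2, above the scale maximum. If 'median' stands for 'mean', each group's labelled centre is off by 2.1 points (0.13 SD) or 2.7 points (0.25 SD), and by 0 for normal scores. This largely cancels in a group difference.

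**2. Precision of the correlation.** Take r = 0.24, about what a 0.5 SD shift gives. Fisher's z interval is tanh(atanh(0.24) ± 1.96/sqrt(138)) = tanh(0.2448 ± 0.1668) = 0.078 to 0.390.

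**3. What r means in points.** d = r/sqrt(p·q·(1 - r²)), with p = 71/141 and q = 70/141. So d = 0.24/sqrt(0.2500 × 0.9424) = 0.494. At SDs of 10, 15 and 20 this is 4.9, 7.4 and 9.9 points.

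**4. What pretest adjustment adds.** Half-width of the 95% interval = 1.977 × SD × sqrt((1 - rho²)(1/71 + 1/70)), where sqrt(1/71 + 1/70) = 0.1684.

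- Unadjusted, SD 15: 1.977 × 15 × 0.1684 = 4.99.
- Adjusted, SD 15, rho 0.5: 4.99 × sqrt(0.75) = 4.33.
- Adjusted, extremes of the range tried: 2.38 (SD 10, rho 0.7) to 6.35 (SD 20, rho 0.3).

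Adjustment also removes bias. With equal SDs at both visits, the regression slope on pretest equals rho. An unadjusted posttest comparison therefore carries rho times any pretest gap between groups: 30%, 50% or 70% of it at rho 0.3, 0.5 or 0.7.

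**5. Point-biserial against a rank-based r.** Simulated groups of 71 and 70 with a 0.5 SD shift in an underlying normal score, expressed on each shape, gave these averages:

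| Shape | Point-biserial | Z/sqrt(N) |
|---|---|---|
| Normal | 0.242 | 0.237 |
| Skew -0.60 | 0.237 | 0.238 |
| Skew -1.25 | 0.226 | 0.237 |

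The sampling SD is about 0.08, so these gaps are negligible. Rank-biserial is on another scale: for normal scores with the same shift it is 2·Phi(0.5/sqrt(2)) - 1 = 0.28.

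**The case against.** **The effect in points is recoverable.** A reader might infer that nobody could work out how many points the training moved. The documents do not support that. If the correlation is between group and posttest score, then r, the two SDs and the group sizes determine the unadjusted mean difference. An approximate interval follows as well: converting 0.078 and 0.390 at SD 15 gives about 2.3 to 12.7 points, close to 7.42 ± 4.99 = 2.4 to 12.4. This stands. However, it yields only the unadjusted difference, and it fails if r is computed on change scores whose SDs are not reported. Change scores would bring in the pretest by subtraction, but the plan does not say they are used. At rho 0.5 they gain no precision over posttest alone, since sqrt(2(1 - 0.5)) = 1.

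**The point-biserial is harmless.** A reader might also infer that a mean-based effect size beside rank tests is a serious error. Under the moderate skews assumed it is not. Larger gaps (0.33 falling to 0.23 and 0.14, with the rank-based value steady at 0.33) appear for a 0.7 SD shift after exponential transformations. Nothing shows that these resemble bounded questionnaire scores. The choice of coefficient is a minor point.

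**'Median' is probably a slip.** It may be. The correction is then one word, but it is still needed. The illustration that overshoots 100 needs a mean near 87, which the documents do not support.

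**Adjustment and clustering are separate issues.** In part. They belong here because they determine which between-group estimate is worth reporting. The number of schools is not stated, so whether an interval can allow for school is unknown.

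**Conclusion.** The point holds as an estimation and reporting fault. The median-with-SD sentence is inconsistent as written on either reading. The only between-group effect size lacks an interval, a stated score (posttest or change) and any use of the pretest, in a design where baseline differences between schools are plausible.

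The size is moderate and rests on assumed values: an unreported interval of roughly 0.08 to 0.39 around r = 0.24, and a half-width of about 4.3 instead of 5.0 points at SD 15 and rho 0.5. The reduction of baseline bias may matter more than the gain in precision, but it depends on a pretest gap that the documents cannot show. Adjustment deals only with the measured pretest; other differences between schools remain, and clustering by school would probably widen every interval above.

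It should not be read as saying that the planned p-values are wrong.

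**What to change.** 1. **Summaries.** Report mean with SD for approximately normal scores and median with interquartile range for non-normal ones. Delete the duplicated paragraph.
2. **Main between-group result.** For each of the four WHOQOL-BREF domains and two PSOC subscales, report the posttest difference in score points adjusted for pretest (ANCOVA). Take the 95% confidence interval and p-value from the same model, so that estimate and test agree. Use bootstrap or robust standard errors if residuals are non-normal. Account for school where the number of schools allows; otherwise state that the interval ignores clustering and is likely too narrow. Keep Mann-Whitney as supportive.
3. **Standardised effect size, if kept.** State which comparison and which scores it describes. Use one named measure, for example rank-biserial 2U/(n1·n2) - 1 beside Mann-Whitney, and give a 95% interval. Rank-biserial and Z/sqrt(N) are not interchangeable (about 0.28 and 0.24 for the same shift).

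The cost is a rewritten analysis section, revised tables and six adjusted differences with intervals. No new data are needed. Because step 2 changes the main test, record it as a dated change to the plan.

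### A normality test on the trial data decides which scores get a rank test, no test is named for scores that pass, and the use of the pre-test score is left open

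*Combined protocol and SAP*

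**What the plan says.** The Data analysis section of the combined protocol and SAP states: "The Kolmogorov-Smirnov test was used to confirm normal distribution". It goes on: "The Wilcoxon and Mann-Whitney U tests were used for continuous variables with non-normal distributions". Categorical variables get a chi-squared test, and the significance rule is "A p-value of less than 0.05 was considered statistically significant". The methods end with "The point-biserial correlation test was used to evaluate the effect size". The whole block is printed twice, with the same content each time.

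No method is named for a continuous variable that the Kolmogorov-Smirnov test does not reject. The section also does not give:

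- the level of that test, or whether the Lilliefors correction is used;
- whether it is applied to pre-test, post-test or change scores, and by group or pooled;
- which of these scores the between-group test compares.

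The Instrument section defines six domain scores: four from the WHOQOL-BREF and two from the PSOC. The Design section describes a controlled before-and-after study, so each mother has a pre-test and a post-test value.

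**The concern.** Read together, the two sentences make a two-stage rule: test normality on the trial data, then use a rank test if it is rejected. This raises three problems.

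- **The choice depends on the data.** A non-significant Kolmogorov-Smirnov result does not confirm normality, and the outcome of the screen depends on details that the plan omits.
- **One branch is empty.** For a score that passes, the analyst must supply a test after seeing the data.
- **The variable to be compared is open.** Post-test scores, change scores and baseline-adjusted scores have different power. Groups were formed by school, not at random, so pre-test means may differ and the three can then also give different estimates.

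Six scores, no named primary outcome and an unblinded assessor leave much room for choice. That can be closed on paper before analysis.

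**Working it through.** **1. The plan's own figure.** The Samples section gives 60 per group, "with an effect size of 0.335" and 80% power. The metric, test and sidedness are not stated. With alpha 0.05, a one-sided matched-pairs Wilcoxon test (efficiency 3/pi against the t-test) gives:

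- effective n = 60 x 3/pi = 57.3
- noncentrality = 0.335 x sqrt(57.3) = 2.536
- power = 0.805, with 60 the smallest n that reaches 80%

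Other variants miss 60: paired t-test 57 (one-sided) or 72 (two-sided), two-sided signed-rank 76, two-sample t-test 111 or 141 per group, Mann-Whitney 117 or 148 per group. The figure suggests that a within-group rank test was in mind. It does not settle the between-group test.

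**2. The rule laid out.**

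| Kolmogorov-Smirnov result | Test named |
|---|---|
| Normality rejected | Wilcoxon, Mann-Whitney |
| Normality not rejected | none |

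**3. Can the empty row be reached?** Simulation with groups of 71 and 70, Lilliefors form at 0.05 in each group, 2,000 replicates. The score shapes are assumptions, since the documents give no SDs. Both groups pass in:

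- 94% of runs for normal scores
- 77% for integer scores like the PSOC (assumed SD 6)
- 29% for skewness 1
- under 1% for a coarse score with an SD of two steps

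The omitted correction also matters. At n = 70, a score with skewness 1 is flagged in about 46% of samples with it and 3% without.

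**4. Does the two-stage rule harm the error rates?** Same simulation, with Welch's t-test assumed for the empty row:

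| | Two-stage | Mann-Whitney fixed |
|---|---|---|
| Type I error | 5.0-5.8% | 4.5-5.9% |
| Power, assumed 0.5 SD shift | 81-88% | 81-89% |

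The error rates barely move. The choice can still change a single result: t and Mann-Whitney disagreed on significance in 4-7% of runs at 0.5 SD, and in 11-12% at 0.335 SD with skewed scores.

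**5. What does the pre-test score contribute?** Assume that 0.335 is a shift in SD units, mothers are independent, the test is two-sided at 0.05, and pre- and post-test SDs are equal with correlation r.

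- Size factor: sqrt(71 x 70 / 141) = sqrt(35.25) = 5.937
- Power is approximately Phi(0.335 / s x 5.937 - 1.96)
- s = 1 for post-test scores, sqrt(2(1 - r)) for change scores, sqrt(1 - r^2) for baseline adjustment

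| Analysis | r = 0.5 | r = 0.7 |
|---|---|---|
| Post-test | s = 1; Phi(0.029) = 51% | s = 1; Phi(0.029) = 51% |
| Change | s = 1; Phi(0.029) = 51% | s = 0.775; Phi(0.608) = 73% |
| Baseline-adjusted | s = 0.866; Phi(0.337) = 63% | s = 0.714; Phi(0.825) = 80% |

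Simulation with normal and skewed (skewness 1) scores agrees:

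- two-stage rule on post-test scores 49-56%, and a fixed t or Mann-Whitney test 48-56%
- Mann-Whitney on change scores 50-55% at r = 0.5 and 72-83% at r = 0.7
- baseline-adjusted regression 62-80%

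**The case against.** The best defence is that rank tests were the intended default. They are the only tests named for continuous variables, medians are reported for all of these, and 60 per group matches a Wilcoxon calculation. One clarifying sentence would then fill the gap, and the error rates in step 4 show little damage meanwhile. This is fair on intent and on error rates. It does not remove the condition written into the text, and it leaves the compared variable unstated.

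A reader might also infer more than the documents support:

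- **That the two-stage rule inflates type I error, or that removing it restores power.** Step 4 shows neither. The gain in step 5 comes from baseline adjustment.
- **That the pre-test score is certainly ignored.** In this design the Wilcoxon test is most naturally the paired one, which uses it, and change scores are not excluded for Mann-Whitney.
- **That ties in the scores dominate the screen.** A Lilliefors flag rate of 91% for a rounded normal score needs an SD of two score steps. It is about 29% at four steps and 14% at six. The PSOC domains span 46 and 36 integer values (9 to 54, 7 to 42), so so narrow an SD is unlikely there.
- **That effect sizes cannot be compared across scores.** One measure, the point-biserial correlation, is stated without any condition on normality.

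It can also be said that baseline adjustment goes further than filling the empty branch requires. That is so, but a between-group analysis has to be named anyway, and the pre-test data are already part of the design.

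**Conclusion.** The point holds as a defect of pre-specification of moderate weight. The choice of test is tied to the trial data, a score that passes the screen has no analysis, and the between-group comparison does not say which score it uses. The cost is freedom to choose after seeing the data, and possibly an unused pre-test score. It is not alpha inflation.

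Under the assumptions of step 5, baseline adjustment gives about 62-80% power, against 49-56% on post-test scores and 50-83% on change scores. The advantage is clear over post-test scores. Over change scores it is clear at a correlation of 0.5 and small or reversed at 0.7. These figures are illustrative: the documents give no SD, no correlation and no metric for 0.335, and clustering by school is ignored. Positive correlation within schools would lower all of them.

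**What to change.** In the Data analysis section:

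1. Delete the Kolmogorov-Smirnov sentence and the condition on non-normality, and remove the duplicated block.
2. State one between-group analysis for all six domain scores, whatever their distribution: post-test score regressed on arm and pre-test score, reporting the adjusted mean difference with its confidence interval.
3. Keep Mann-Whitney on change scores, for every score, as a labelled sensitivity analysis.
4. Check residuals by plot, and state that the result does not switch the primary test.
5. If outcome data have already been seen, date the change and label it as made afterwards.

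The cost is a few sentences and no new data. There are two downsides. A mean difference is reported for scores that may be skewed, and the rank test on change scores can be slightly more powerful when scores are skewed and the correlation is high (up to about 83% against 80% in the simulations). The sensitivity analysis covers both. Adjusting for the pre-test score does not remove other differences between the schools.

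### Arms follow convenience-sampled schools, yet the score tests and effect size are unadjusted and the pretest has no stated between-arm role, so a baseline school difference can be reported as a training effect

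*Combined protocol and SAP*

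**What the plan says.** The Design section states: "This study used a quasi-experimental design, which was conducted based on a pretest-posttest control group". The Samples section says that the mothers were "divided into intervention (N=71) and control group (N = 70) according to a special school using a convenience sampling method". No randomisation or matching is described, and the number of schools is not given.

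Under Intervention, "The control and intervention groups were given a parenting guidebook for children with ID"; only the intervention arm also attends the weekly training.

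Under Data analysis, "The Wilcoxon and Mann-Whitney U tests were used for continuous variables with non-normal distributions", and "The point-biserial correlation test was used to evaluate the effect size". Chi-squared is kept for qualitative variables. The section does not say:
- which variable the Mann-Whitney test compares (post-test score or change from pretest);
- whether the Wilcoxon test (presumably the paired, within-arm one) or the between-arm test carries the conclusion;
- what happens if the arms differ at pretest.

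No covariate, adjusted model or school term is named.

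**The concern.** When arms are formed from intact schools chosen by convenience, nothing in the allocation makes pretest scores comparable. Schools may differ in catchment, support for families or severity mix, and parents' scores may differ with them. A pretest was built into the design, but the analysis never says how it enters the between-arm comparison.

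Three readings are open, and each can go wrong:
- **Post-test Mann-Whitney** carries over whatever part of a baseline gap is still present at post-test.
- **Change-score Mann-Whitney** cancels a gap that stays constant, but is biased if the gap shrinks or grows.
- **Within-arm Wilcoxon** detects any improvement, including improvement from the guidebook, from retesting or from time, all of which the control arm shares.

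The point-biserial correlation on post-test scores has the same weakness as the post-test comparison. Leaving the choice open also allows it to be made after the results are seen.

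**Working it through.** **Inputs from the plan.** 71 and 70 mothers; significance at p < 0.05 (sidedness not stated, taken as two-sided); effect size 0.335 (metric not stated).

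**Assumed, because the plan gives no figure.** Within-arm SD 1; pretest gap *g* = 0.3-0.5 SD; pre-post correlation *r* = 0.5-0.7; normal scores; no clustering; no training effect.

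**Bias.** Let the post-test gap be *k·g*, where *k* = 1 means the gap persists, *k* = 0 that it disappears, and *k* = *r* that it acts only through the pretest. The spurious effect is:
- post-test: *k·g*
- change score: (*k* − 1)·*g*
- ANCOVA on the pretest: (*k* − *r*)·*g*

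**Rejection rate.** With c = √(71 × 70 / 141) = 5.937 and the usual efficiency factor √(3/π) = 0.977 for Mann-Whitney on normal data, the expected test statistics are:
- z(post) = *k·g*·c·0.977
- z(change) = (*k* − 1)·*g*·c·0.977 / √(2(1 − *r*))
- z(ANCOVA) = (*k* − *r*)·*g*·c / [√(1 − *r*²)·√(1 + *g*²c²/139)]

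The rejection rate is Φ(|z| − 1.96) + Φ(−|z| − 1.96).

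Worked case, *g* = 0.5, *r* = 0.5, gap persists:
- z(post) = 0.5 × 5.937 × 0.977 = 2.90, giving 83% (simulated 82%).
- z(change) = 0, giving 5%.
- z(ANCOVA) = 0.25 × 5.937 / (0.866 × 1.031) = 1.66, giving 38% (simulated 37%).

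Simulated ranges over the four combinations of *g* and *r*:

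| Course of the gap | Post-test Mann-Whitney | Change-score Mann-Whitney | ANCOVA |
|---|---|---|---|
| Persists | 41-84% | about 5% | 11-37% |
| Acts only through pretest | 14-53% | 10-31% | 5-6% |
| Halves | 14-30% | 14-46% | 5-13% |
| Disappears | 5% | 40-96% | 17-79% |

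With a gap of only 0.1 SD, over the same four cases, the rates are 5-9%, 5-12% and 5-9%.

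These are two-sided rejections. A gap in favour of the intervention schools inflates the post-test contrast. If that gap shrinks, it biases the change score the other way, and the signs reverse if the control schools start higher.

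**Effect size.** From a post-test gap *d* alone, point-biserial r = *d* / √(*d*² + 141 × 139 / (71 × 70)). The last term is 3.94, so *d* = 0.5 gives 0.5 / √4.19 = 0.24 with no training effect.

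**Within-arm test.** If both arms improve equally by 0.2-0.3 SD, z = *m*·√71·0.977 / √(2(1 − *r*)). For *m* = 0.2, *r* = 0.5 this is 1.65, or 38% (simulated 37%). Over the assumed range the intervention-arm Wilcoxon is significant in 37-88% of simulated trials, and in that arm only in 10-26%.

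**Power, if 0.335 is Cohen's d and there is no gap or clustering.** On normal scores z(post) = 0.335 × 5.937 × 0.977 = 1.94, so power is 0.49. Simulated values:

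| Correlation | Post-test Mann-Whitney | Change-score Mann-Whitney | ANCOVA |
|---|---|---|---|
| 0.5 | 0.49 | 0.49 | 0.62 |
| 0.7 | 0.49 | 0.70 | 0.79 |

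On assumed lognormal scores ordinary ANCOVA has 0.68-0.81, post-test Mann-Whitney 0.93-0.94 and rank-based ANCOVA 0.98-1.00.

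**The case against.** The strongest reply is that the plan already permits a sound analysis. With intact schools a stable difference in level is a plausible threat, and change-score Mann-Whitney then holds 5% while ANCOVA rejects in 11-37%. Making ANCOVA primary is thus a judgement about how gaps evolve, and the documents cannot settle it. This stands, and it is why the change-score analysis belongs beside ANCOVA. It does not rescue the plan as written, which does not commit to change scores, and the two readings fail in opposite situations. For a post-test gap between zero and *g*, the largest bias is *g* for post-test scores, *g* for change scores and 0.5*g*-0.7*g* for ANCOVA at correlations of 0.5-0.7. If the gap widens, ANCOVA is more biased than the change score.

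A second reply is that adjustment may cost power. A reader might infer from the normal-score figures that it never does. The documents do not support that: the plan invokes these tests for non-normal scores, where ordinary ANCOVA can lose substantial power. The rank-based version did not lose power in the skewed case tried. Even on normal scores, the gain over change-score Mann-Whitney at correlation 0.7 is only about 0.09.

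A third reply is that nothing says the within-arm Wilcoxon carries the conclusion. That is correct. A reader might infer otherwise because 60 per group can be reproduced as a one-sided within-group signed-rank test at 0.335, whereas a two-group comparison with 0.335 as Cohen's d needs 111-148 per group. The plan states neither test, metric nor sidedness for that calculation, so this remains a guess. Chi-squared is also unadjusted, but both outcomes are scores, so it most plausibly serves participant characteristics and is not part of this point.

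**Conclusion.** The point holds in this form. Allocation follows convenience-sampled schools, the tests and effect size named for the scores are unadjusted, and the pretest's role between arms is unstated. Followed as written, the plan can report a baseline school difference as a training effect, and a within-arm result cannot separate training from guidebook.

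The size cannot be derived from the documents, which give no baseline gap, SD, correlation or number of schools. Under the assumed 0.3-0.5 SD gap, the post-test reading rejects a true null in up to about 84% of trials if the gap persists; with a 0.1 SD gap the excess is small. Clustering by school was left out and would raise the rates.

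Two stronger conclusions are not supported. The bias is possible but not inevitable, since the plan does not fix the post-test reading and no baseline gap is known. Nor does pretest adjustment cure the problem: ANCOVA stays biased if the gap persists, widens or disappears, and no analysis here removes unmeasured school-level confounding. This is an inexpensive improvement to the plan and does not show that its result is wrong.

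**What to change.** In the Data analysis section, before the arms are compared:

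1. State that the conclusion rests on the between-arm contrast, and label within-arm Wilcoxon tests descriptive.
2. For each score, pre-specify as primary a between-arm comparison of the post-test adjusted for the same pretest score. Use rank-based ANCOVA for the test if scores are non-normal.
3. Report the adjusted difference with a 95% CI (bootstrap if skewed) as the effect measure, in place of the unadjusted point-biserial correlation.
4. Pre-specify the between-arm change-score comparison as a sensitivity analysis. State what each method assumes about how a baseline gap evolves, and report any disagreement.
5. Report baseline scores by arm. State that neither analysis removes unmeasured school-level confounding or differing trends between schools.

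The cost is SAP wording and one primary and one sensitivity analysis per score; the pretest is already part of the design, so no new data are needed. The downside is a little more analysis work and open reliance on an assumption about the baseline gap. Any statement that adjustment costs no power should be limited to normal scores or the rank-based version.

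### No primary outcome, deciding comparison or multiplicity rule: false benefit is about 5–14% if six domain scores are tested at 0.05, or 4–5% with one score per instrument, against 2.5% for one test

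*Combined protocol and SAP*

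**What the plan says.** The Design section states "This study used a quasi-experimental design, which was conducted based on a pretest-posttest control group".

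The Instrument section defines the outcomes by domain. "The WHOQOL-BREF consists of four domains (physical health, psychological, social relationships, and environment) with 26 questions", and "The total score for each domain is transformed to a scale of 0-100 according to the scoring guidelines". For parenting, "The PSOC consists of the domains of satisfaction and self-efficacy with parenting", each with its own score range. That makes six scores. No total is defined for either instrument.

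The Data analysis section gives the tests and the threshold: "The Wilcoxon and Mann-Whitney U tests were used for continuous variables with non-normal distributions", and "A p-value of less than 0.05 was considered statistically significant". It adds that effect size is assessed with a point-biserial correlation. The text of this section is printed twice. Neither copy names a primary score, says which comparison decides benefit, says whether the between-arm outcome is the post-test or the change score, or mentions multiplicity.

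The Samples section sizes the study at a minimum of 60 per group for an effect of 0.335 and 80% power. It names no outcome, test, alpha or sidedness. The Intervention section states "The control and intervention groups were given a parenting guidebook for children with ID".

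**The concern.** Followed as written, the plan lets benefit be claimed from any one domain that reaches p<0.05. It does not exclude claiming benefit from a pre-post change in the intervention arm alone. Two things are at stake.

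- **Multiplicity.** With several scores and no adjustment, the chance that at least one favours training by luck exceeds the rate for a single test.
- **Which comparison decides.** Both arms received the guidebook, and both are measured twice. A change within the trained arm mixes any training effect with the guidebook, repeat measurement and time. Only the contrast with the control arm speaks to the training.

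**Working it through.** **1. The plan's own figure.** Inputs from Samples: effect 0.335, 80% power, 60 per group. Alpha 0.05 is assumed, from the Data analysis threshold.

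- Two groups, standardised difference, normal approximation: n = 2(z₁₋α + 0.842)²/0.335². Two-sided: 2 × (1.960 + 0.842)²/0.1122 ≈ 140 per group (141 by exact t). One-sided: 2 × (1.645 + 0.842)²/0.1122 ≈ 111.
- Mann-Whitney, dividing by the relative efficiency 3/π = 0.955: 148 two-sided, 117 one-sided.
- Paired t: 72 two-sided, 57 one-sided. Paired signed-rank with the same factor: 76 two-sided, **60 one-sided** (power 80.5%).
- Point-biserial r = 0.335: 65 in total two-sided, 51 one-sided. Two-group ANOVA with f = 0.335: 72 in total.

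Among these variants only the one-sided paired signed-rank test returns 60. The sizing therefore does not identify a between-arm comparison as the deciding one.

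**2. False benefit over several between-arm tests.** Assumptions: two-sided 0.05 per test (0.025 in the favourable direction), no true effect, valid p-values, and a common correlation ρ between test statistics. The documents give neither ρ nor sidedness.

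Independent scores: 1 − 0.975⁶ = 0.141 for six; 1 − 0.975² = 0.049 for two. Correlated scores, k tests: 1 − ∫ φ(x) Φ((1.96 − √ρ·x)/√(1−ρ))ᵏ dx.

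| ρ | Six tests | Two tests |
|---|---|---|
| 0 | 14.1% | 4.9% |
| 0.3 | 12.2% | 4.8% |
| 0.5 | 10.4% | 4.5% |
| 0.7 | 8.2% | 4.2% |
| 0.9 | 5.4% | 3.5% |

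One pre-named test gives 2.5%. A million-draw simulation of the six-test case agreed (14.1%, 10.4% and 5.4% at ρ = 0, 0.5 and 0.9). If tests were one-sided at 0.05, the six-test range would be 26% (ρ = 0) to 10% (ρ = 0.9), against 5%.

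**3. A within-arm test.** Take the intervention arm, n = 71, and a signed-rank test of one domain. Assume both arms shift by 0.2 SD of change with no training effect. The expected test statistic is about 0.2 × √(71 × 0.955) = 1.65, so the chance of p<0.05 in favour is about P(Z > 1.96 − 1.65) ≈ 0.38. Simulation gives about 37%. At shifts of 0.1 and 0.3 SD simulation gives about 12% and 68%. These rates are for any given single domain, not for at least one of six.

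**4. What adjustment does.** Holm over six starts at 0.05/6 = 0.0083. False benefit becomes 2.5% at ρ = 0, 2.1% at 0.5 and 1.1% at 0.9.

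**The case against.** **The six-test count is a reading, not a statement.** The title names two constructs, each tied to one instrument, and the plan never says that the domains are tested separately. With one score per instrument the excess is modest, 4–5% against 2.5%. This stands as a limit on size. Six remains the more natural reading, because only domain scores are defined.

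**The plan does lean towards a between-arm comparison.** It has a control group, and a point-biserial correlation needs a two-level variable, most naturally study arm. That is fair, but it does not settle the matter: the two levels could be pretest and posttest, and the sizing points elsewhere.

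**A reader might infer that the sponsor planned a one-sided within-arm test**, since that alone reproduces 60. The documents do not support this. They name no test or sidedness for the sizing, and a match under an assumed alpha is not evidence of intent. Nor do they say that the Wilcoxon test is for pre-post change within an arm; that is inferred from the design.

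**For a small non-randomised study, unadjusted p-values labelled exploratory could be defended.** They could, if the plan said so. It does not call itself exploratory, and it sets a formal sample size and significance threshold.

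**Allocation by school and unblinded assessment may matter more.** They are separate problems, and nothing here repairs them.

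**Conclusion.** The omission is real and should be corrected. With six two-sided between-arm tests, no true effect and otherwise valid p-values, the chance of at least one false benefit is about 14% (correlation 0) to 5% (0.9), against 2.5% for one test. With one score per instrument it is 4–5% (correlation 0 to 0.7). Separately, a shared shift of 0.2 SD of change (assumed) would make any given domain significant within the trained arm in about 37% of trials with no training effect.

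A reader might want to go further and put a number on the extra inflation from allocation by school. The documents do not allow it. The number of schools is not given, and the groups of 10 are training groups in the intervention arm, not the unit of allocation. All that can be said is that the rates above take each test as valid, which allocation by school without randomisation does not guarantee.

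**What to change.** In Data analysis:

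1. Base every claim of effect on between-arm contrasts. Report within-arm pre-post tests as descriptive only.
2. Use one outcome form that takes account of the pretest for all domains: Mann-Whitney on change scores, or a baseline-adjusted comparison. Do not use the post-test alone. Schools were not randomised, so a baseline difference between arms would be counted as effect.
3. Report all six contrasts with Holm-adjusted p-values at an overall two-sided 0.05. Alternatively, and only if outcomes are still unseen, name one primary score per instrument, apply Holm over the two, and label the rest secondary.
4. If outcomes have been seen, report all six with Holm and state when the rule was added. The document does not settle which case applies: it is dated 20 December 2024 but describes in the past tense data collected from January to August 2025.
5. State that Holm addresses multiplicity only and does not correct for allocation by school or non-random assignment.

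**Cost.** A few sentences and no new data. The price is power at Holm's first step, shown for 71 v 70 and ignoring clustering. The plan does not say what kind of effect size 0.335 is, so both readings are illustrations.

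| Meaning of 0.335 | One test, 0.05 | Holm over two, 0.025 | Holm over six, 0.0083 |
|---|---|---|---|
| Standardised difference | 51% | 39% | 25% |
| Point-biserial r (d = 2 × 0.335/√(1 − 0.335²) = 0.711) | 99% | 97% | 94% |
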